8.3 Enrollment

This is an open-label study and parallel (simultaneous) enrollment is allowed for all Cohorts.

8.4 Endpoints

8.4.1 Safety Endpoints

Safety endpoints include adverse events, concomitant medications, laboratory measurements, ECGs, physical examinations, and vital signs.

8.4.2 Pharmacokinetic Endpoints

The primary study analysis variables are the telavancin PK parameters: C_{max} , T_{max} , AUC_{0-t} , AUC_{0-inf} , and $t_{1/2}$ (as appropriate) derived from the plasma concentration-time data.

8.5 Statistical Analysis

8.5.1 General Considerations

Unless otherwise specified, results will be tabulated and summarized descriptively; all individual subject data will be fully listed.

The number and percentage of patients will be presented for categorical variables while mean, median, standard deviation and range (minimum and maximum) will be presented for continuous variables.

The statistical package SAS (C

ary, North Carolina) will be used to produce summary tables and subject listings related to demographics, baseline characteristics, patient disposition and safety assessment.

8.5.2 Handling of Missing Data

Unless otherwise specified, missing values will not be imputed.

8.5.3 Analysis Populations

Two analysis populations will be defined:

- Safety population: all subjects who receive any amount of study drug.
- PK population: all subjects who receive any amount of study drug and who provide PK data from at least one post-dose plasma sample.

8.5.4 Demographics, Baseline Characteristics and Patient Disposition

Summary of demographics and baseline characteristics will include all subjects from the Safety population. The number of subjects discontinuing the study prematurely and the reason for discontinuing will be summarized based on the Safety population.

8.5.5 Safety

All safety assessments will be conducted on the Safety population.

Treatment-emergent adverse events (TEAEs) are defined as AEs with onset on or after initiation of study medication. The number and percentage of patients reporting TEAEs will be tabulated by Medical Dictionary for Regulatory Activities (MedDRA[®], version 16 or a more recent version) system organ class and preferred term, severity, and relationship to study medication. Serious TEAEs and TEAEs resulting in discontinuation of study drug will be summarized separately.

Concomitant medications will be mapped using the WHODRUG dictionary (WHODDE B2 format, March 2013 or a more recent version). The number and percentage of patients taking each concomitant medication will be tabulated.

Analysis of laboratory results will be based on those reported by the local laboratory. Continuous laboratory measurements will be descriptively summarized at each visit for observed values and changes from baseline. Categorical laboratory measurements will be summarized by the number and percentage of patients with low, normal and high values based upon the normal ranges provided by each local laboratory. If a normal range is missing for a particular local laboratory then the normal “textbook range” will be used. A shift

table of laboratory measurements comparing pre- and post-treatment values relative to normal ranges (for example, normal to low, normal to normal, or normal to high) will also be summarized.

Vital signs and ECG parameters (based on average of multiple measurements if measured) will be summarized at each visit for observed values and changes from baseline. In addition, QT and QTc intervals will be summarized categorically as number and percentage of patients with abnormal values or increases.

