6.3.1 Screening

The screening visit will be performed within 48 hours before planned dosing. Screening activities will comprise the following:

- Written, signed, and dated informed consent must be obtained after the nature of the study has been explained to the legally authorized representative and subject, if applicable, and before any study procedures are performed. Where applicable, assent will also be obtained based on local IRB requirements.
 - Review of inclusion and exclusion criteria (Subjects will be eligible for enrollment only if they meet all the inclusion and none of the exclusion criteria)
 - Medication and medical history
-

- Height and weight
- Vital signs
 - Heart rate (HR) and blood pressure (BP)
 - Respiratory Rate (RR) and body temperature
- ECG (12-lead)
- Physical examination as outlined in Section 6.4.3.4
- Blood collection (NOTE: If standard clinical laboratory tests have been performed within the protocol-specified windows for laboratory testing at screening, the results may be used to avoid excessive blood draws.)
 - Hematology
 - Serum chemistry
 - Serum pregnancy test (for females who are post menarche)
- Urine collection for urinalysis
- Concomitant medications
- Adverse events

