6.4.3 Safety Assessments

6.4.3.1 Adverse Events

Adverse events (AEs) will be recorded from the time of consent through the follow-up visit for each subject. AEs may be observed by the site study personnel or spontaneously reported by the subject or reported in response to a standard question from site study personnel and include any protocol-related event.

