6.4.3.2 Medical History

A complete medical history will be taken during the Screening Visit and will include evaluation for past and present cardiovascular, respiratory, gastrointestinal, renal, hepatic, neurological, endocrine, lymphatic, hematologic, immunologic, dermatologic, psychiatric, and genitourinary diseases, surgical history, or any other diseases or disorders. Medical events or conditions that arise or worsen in severity or frequency following telavancin administration will be recorded as a (Treatment Emergent Adverse Event) TEAE.

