7.2 Adverse Event Definition for the Purposes of This Study

For the purposes of this the Sponsor clinical study, adverse events will be defined as follows:

An adverse event (AE) is any untoward medical occurrence in a subject who has signed an informed consent form and is participating in a clinical investigation. An AE can be any unfavorable and unintended sign (including an abnormal laboratory finding), symptom, or disease, whether or not considered related to the study drug (investigational product).

Preexisting events that increase in frequency or severity or change in nature during or as a consequence of participation in clinical studies will also be considered as adverse events. An AE may also include pre- or post-treatment complications that occur as a result of a protocol-mandated procedure (such as a biopsy).

Any medical condition or clinically significant laboratory abnormality with an onset date prior to the time the subject signed the informed consent form is considered to be preexisting and should be documented in the medical history CRF, if applicable for the study.

Whenever possible, the diagnosis (rather than a series of terms related to a diagnosis) should be recorded as the AE term.

An AE does not include the following:

- Medical or surgical procedures (such as surgery, endoscopy, tooth extraction, or transfusion); the condition that leads to the procedure is an adverse event
 - Preexisting diseases or conditions present or detected before signing an informed consent form that do not worsen
-

- Situations where an untoward medical occurrence has not occurred (such as hospitalization for elective surgery or social and/or convenience admissions)
- Overdose of either study drug or concomitant medication without any signs or symptoms, unless the subject is hospitalized for observation

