7.3 Assessment of Adverse Events

All AEs will be assessed by the investigator and recorded in the case report form, including the dates of onset and resolution, severity, relationship to study drug, outcome, and action taken with study medication.

Clinical severity should be recorded and graded using mild, moderate or severe as described below.

Mild	= Awareness of signs or symptoms, but easily tolerated
Moderate	= Discomfort sufficient to cause interference with usual activities
Severe	= Incapacitation with inability to work or perform usual activities

The relationship to study drug therapy should be assessed using the following definitions:

- **Not Related:** Evidence exists that the adverse event has an etiology other than the study drug (such as a preexisting condition, underlying disease, intercurrent illness, or concomitant medication).
- **Possibly/Probably Related:** A temporal relationship exists between the event onset and administration of the study drug. It cannot be readily explained by the subject's clinical state or concomitant therapies and appears **with some degree of certainty** to be related based on the known therapeutic and pharmacologic actions of the drug. In case of cessation or reduction of the dose, the event abates or resolves and reappears upon rechallenge. It should be emphasized that ineffective treatment should not be considered as causally related in the context of adverse event reporting.

These criteria in addition to good clinical judgment should be used as a guide for determining the causal assessment. If it is felt that the event is not related to study drug therapy, then an alternative explanation should be provided.

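### The TEAE definition in Section 8.5.5 has no worsening clause, unlike Section 6.4.3.2, so an AE that starts between consent and dosing and worsens after the dose may be left out of the TEAE tables

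*Combined protocol and SAP*

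**What the plan says.** The protocol describes a TEAE in two places. In Section 8.5.5 (Safety), TEAEs "are defined as AEs with onset on or after initiation of study medication". In Section 6.4.3.2 (Medical History): "Medical events or conditions that arise or worsen in severity or frequency following telavancin administration will be recorded as a" TEAE. The second has a worsening limb and the first does not.

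Three other sections decide whether the difference matters:

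- Section 6.4.3.1 sets the collection period: "Adverse events (AEs) will be recorded from the time of consent through the follow-up visit for each subject". Section 6.3.1 adds: "The screening visit will be performed within 48 hours before planned dosing". Collection therefore begins before the dose.
- Section 7.2 counts as adverse events "Preexisting events that increase in frequency or severity or change in nature during or as a consequence of participation in clinical studies". In the same section, a condition "with an onset date prior to the time the subject signed the informed consent form is considered to be preexisting".
- Section 7.3 lists what is recorded for each AE, "including the dates of onset and resolution, severity, relationship to study drug", followed by outcome and action taken. It lists no date of worsening and no TEAE flag.

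The AE tables in Section 8.5.5 (by system organ class and preferred term, severity and relationship) are restricted to TEAEs. So are the separate summaries of serious events and of events leading to discontinuation of study drug. Section 8.5.1 provides full listings of individual subject data.

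**The concern.** Safety and tolerability is the secondary objective, and the TEAE tables are its main AE summary. If the tables use a narrower definition than the recording section, an event that the protocol calls treatment-emergent can be absent from them. The difference runs in one direction: adding a worsening limb can only add events, so compared with Section 6.4.3.2 the onset-only rule can only lower the count. The severity table would also lose the post-dose grade of any event left out. Several reactions that Section 1.4 reports from single-dose studies, such as nausea, headache, pruritus and fatigue, are non-specific. A mild symptom before the dose that becomes moderate or severe after it is therefore conceivable in this population.

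**Working it through.** There is no stated figure to reproduce. The check sets the definitions against each possible time of onset, for an event that worsens after the dose.

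| Onset of the event | Section 6.4.3.2 | Section 7.2 | Section 8.5.5, read literally |
|---|---|---|---|
| Before consent | TEAE (worsened) | Preexisting; the worsening is itself an AE | Counted if that AE is dated from the worsening |
| After consent, before dose | TEAE (worsened) | Not preexisting; worsening rule does not apply | Not counted if the AE keeps its original onset date |
| On or after dose | TEAE (arose) | AE | Counted |

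**Can the middle row occur?** Yes. Recording starts at consent, consent is a screening procedure, and screening may be up to 48 hours before planned dosing. The gap is at most about 48 hours wide.

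**Does another section close it?** Section 7.2 does not, because its worsening rule is written for preexisting events. Section 7.3 does not, because nothing there says that a rise in grade opens a new record or resets the onset date. With no TEAE field among the listed items, TEAE status would presumably be derived from the onset date under Section 8.5.5.

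**Scale.** The effect of one omitted child on an incidence is 1/n. The planned numbers come from Section 8.2.

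- All subjects, n = 30: 1/30 = 3.3 percentage points.
- An older age cohort, n = 8: 1/8 = 12.5 points.
- The infant cohort, n = 6: 1/6 = 16.7 points.

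Section 8.5.5 does not specify AE tables by age cohort; Section 8.5.6 specifies age stratification for the PK summaries. The 3.3-point figure is therefore the one that matches the written plan. It changes a given row only if the child has no other event that qualifies for that row. The number of such events is not given, so the total effect cannot be computed.

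**The case against.** The strongest reply is that Sections 6.4.3.2 and 8.5.5 work in sequence: the first says what is recorded, the second tabulates it. The worsening limb in Section 6.4.3.2 is not limited to conditions that precede consent. If a site enters the worsening as its own event dated after the dose, the entry meets the Section 8.5.5 definition and is counted. This reading is available. A reader might infer that these events are certain to be dropped, and the documents do not support that, because nothing says the AE must keep its pre-dose onset. Equally, nothing tells sites to open a new record, so the reading does not settle the matter.

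A second reply is that most symptoms of the presenting illness will predate consent, where Section 7.2 already makes worsening an AE. This also stands. It limits the point to events that first appear between consent and dose, and the documents do not show that such events are common.

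A third reply is that the safety information survives elsewhere, and largely it does. Individual listings show the event. Laboratory shift tables and the laboratory, vital-sign and ECG changes from baseline do not depend on TEAE status. SAEs are reported from consent regardless of cause (Section 7.6). The stopping rules in Table 4 use suspected drug-related reactions. The study has one arm and descriptive safety summaries, so the definition cannot bias a comparison or a test. What remains is the content of the AE tables.

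**Conclusion.** The point holds as a minor inconsistency. The two definitions differ, and for an AE that starts between consent and dose and worsens afterwards, the documents do not determine whether it enters the TEAE tables. Read literally, Section 8.5.5 leaves it out, and any error is an undercount relative to Section 6.4.3.2.

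The size is about 3.3 percentage points per omitted child on the planned 30 subjects, with an unknown and possibly zero number of such children. A reader might take the effect to be 12.5 to 16.7 points, but that holds only if the tables are also split by age cohort, which Section 8.5.5 does not plan. The conclusion rests on two assumptions: that TEAE status is derived from the recorded onset date, and that a worsening event keeps its original record. Neither is stated or excluded.

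**What to change.** Use one definition in Sections 6.4.3.2 and 8.5.5: an AE with onset on or after the start of study medication, or one with earlier onset that worsens in severity or frequency afterwards.

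The definition alone is not enough, because Section 7.3 lists no date of worsening. State there that a post-dose worsening is entered as a new AE record with its own onset date and severity.

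The cost is a short protocol wording change and a CRF completion instruction. The TEAE count may rise slightly. No sample size, visit or assessment changes.

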8.5.6 Analysis of Pharmacokinetics

For all PK data analyses, the PK population will be used.

Individual and mean drug concentration versus time curves for telavancin and its metabolite, AMI-11352, will be presented by subgroup. Summary statistics (mean, standard deviation, minimum, maximum, number of subjects, and coefficient of variation) will be calculated for plasma concentrations for each time point and pediatric age subgroup.

Plasma telavancin concentration-time data will be used to obtain T_{max} , C_{max} , AUC_{0-t} , AUC_{0-inf} , and $t_{1/2}$ (as appropriate).

Noncompartmental and/or population PK modeling methods will be used for determination of plasma PK parameters. All PK parameters will be presented by individual listings and summary statistics according to age stratification (e.g., mean, geometric mean, median, standard deviation, 95% confidence interval, coefficients of variation, minimum, maximum, and number of subjects). Further analysis of the potential relationship between PK parameters and subject age may be performed. Plasma concentration data may also be utilized for development of a pediatric population PK model.

In the first step of the population PK model development for this analysis, the full population PK model from adults will be modified to incorporate the expected alteration in renal function with age in the pediatric population {6}. This modified model will then be used to simulate expected telavancin concentration-time profiles in adolescent patients receiving the planned dose of 10 mg/kg in order to ensure that the resultant PK exposures (C_{max} and AUC) are consistent with those observed in adult patients administered telavancin in previous clinical studies. Once the study has begun enrollment, a modified population PK model will be fit to the telavancin plasma concentration-time data from the first set of eight subjects in order to

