Appendix 5: Schwartz Equation for Estimated Creatinine Clearance

The estimated creatinine clearance will be calculated using the Schwartz equation {5, 7} as follows:

$$\text{creatinine clearance (mL/min/1.73m}^2\text{)} = \frac{k \times \text{height or length (in cm)}}{\text{serum creatinine (in mg/dL)}}$$

Where k = constant of proportionality that is age-specific:

- k = 0.55 for subjects 1 to 12 years
- k = 0.55 for female subjects >12 years
- k = 0.70 for male subjects >12 years

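### Section 8.5.5 does not relate creatinine to age or to the child's own baseline, so a 1.5- to 2-fold rise in a small child may not show in the summary tables

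*Combined protocol and SAP*

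**What the plan says.** Section 8.5.5 plans three laboratory summaries.

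- Continuous: "Continuous laboratory measurements will be descriptively summarized at each visit for observed values and changes from baseline". Absolute difference is the ordinary reading, because no ratio or percent change is named, but the word absolute does not appear.
- Categorical: "Categorical laboratory measurements will be summarized by the number and percentage of patients with low, normal and high values based upon the normal ranges" of each local laboratory. The fallback is a textbook range: "If a normal range is missing for a particular local laboratory". Neither range is stated to be specific to age or sex.
- Shift: a "table of laboratory measurements comparing pre- and post-treatment values relative to normal ranges".

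On grouping, the section says only that "All safety assessments will be conducted on the Safety population". Sections 8.5.1 and 8.5.4 and the synopsis add no age stratum for safety. Section 8.5.6 does specify one for PK, where summary statistics "will be calculated for plasma concentrations for each time point and pediatric age subgroup".

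For QT and QTc, Section 8.5.5 also plans counts of abnormal values or increases. Creatinine has no counterpart. Scheduled post-dose chemistry is on Day 2 only (Table 1, Section 6.3.3), and the follow-up contact includes no laboratory tests (Section 6.3.4).

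**The concern.** Creatinine depends on body size. A low/normal/high category carries the same meaning in an infant and an adolescent only if the range fits the child, and a difference in mg/dL means a different proportional loss of clearance at each size. The plan already treats renal function as age-dependent elsewhere: Schwartz clearance at entry, reduced clearance at 1 to 2 years in the simulations (Section 3.3), and age-related renal function in the PK model (Section 8.5.6). The safety tables do not carry that through.

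Renal effects are a known concern with this drug. With one scheduled post-dose creatinine per child, a shift table showing no movement could be read as reassurance about the youngest children when it was not sensitive enough to provide it.

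**Working it through.** The plan states no creatinine limit or expected change, so there is no figure of its own to reproduce. The check uses the Appendix 5 formula.

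**Inputs from the plan.** Clearance = k × height / creatinine, with "k = 0.55 for subjects 1 to 12 years", k = 0.55 for females over 12 and k = 0.70 for males over 12. Six infants among about 30 subjects. Exclusion below 50 mL/min/1.73 m².

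**Assumed inputs.** Heights 75 cm (infant), 165 cm (adolescent girl) and 170 cm (adolescent boy). Baseline clearance 120, with 102 as a sensitivity case (120 × 0.85, borrowing the 15% reduction in Section 3.3). Upper limit of normal 0.5 to 1.0 mg/dL.

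**1. Baseline creatinine = k × height / clearance, at 120**

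- Infant: 0.55 × 75 / 120 = 0.344 mg/dL
- Girl: 0.55 × 165 / 120 = 0.756 mg/dL, or 2.2 times the infant
- Boy: 0.70 × 170 / 120 = 0.992 mg/dL, or 2.9 times the infant

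At clearance 102 the infant's baseline is 41.25 / 102 = 0.404 mg/dL.

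**2. Largest rise that still reads normal = upper limit / baseline**

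| Upper limit (mg/dL) | From 0.344 | From 0.404 |
|---|---|---|
| 0.5 | 1.45-fold | 1.24-fold |
| 0.7 | 2.04-fold | 1.73-fold |
| 1.0 | 2.91-fold | 2.47-fold |

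From 0.344, a 1.5-fold rise gives 0.516 and a doubling gives 0.688. With a limit of 0.5 both are flagged high. With 0.7 both read normal, the doubling by a margin of only 0.01. With 1.0 both read normal. From 0.404, a doubling (0.809) is flagged at 0.7, while a 1.5-fold rise (0.607) is not.

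Lower baselines leave more room. With a limit of 0.5, a 1.5-fold rise stays normal from any baseline up to 0.5 / 1.5 = 0.33, and a doubling up to 0.5 / 2 = 0.25.

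**3. What normal can conceal.** At 0.7 mg/dL the infant's clearance is 41.25 / 0.7 = 59, down from 120. The exclusion threshold of 50 corresponds to 41.25 / 50 = 0.825 mg/dL, so a limit above that would label as normal a value at which this child could not have been enrolled.

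**4. Pooled change from baseline**

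- One infant doubling: 0.344 / 30 = 0.011 mg/dL in the overall mean, against 0.344 / 6 = 0.057 in the infant cohort
- All six doubling: 6 × 0.344 / 30 = 0.069 overall, against 0.344 in the cohort

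**5. Pooled maximum.** Section 8.5.1 also gives the minimum and maximum, so one doubling would put the maximum at 0.34 or more. That figure does not identify a doubling: the same +0.344 is (0.992 + 0.344) / 0.992 = 1.35-fold in the boy.

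**The case against.** The strongest reply is that the documents already provide several routes to the same finding. Section 8.5.1 requires full individual listings, and with about 30 children each pre/post pair can be read. The Safety Data Review Committee sees laboratory results together with demographics (Section 6.5). Abnormal findings judged clinically significant that meet the AE definition must be recorded as AEs (Section 7.5), whatever their range category. All of this stands. A reader might infer that a renal signal in the youngest would be lost, and the documents do not support that. These routes rely on reading listings or on investigator judgement, however, and do not replace a prespecified summary.

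A reader might also infer that a 1.5- to 2-fold rise would always read normal to normal. It would not. The upper limit is assumed, nothing says that the local ranges are adult ones, and a tight paediatric range would catch many such rises. A lower baseline clearance also shortens the headroom. What remains is that the plan does not require suitable ranges.

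Nor do the adult renal rates carry over directly. The 3% and 10% figures (Section 1.1) come from Phase 3 treatment trials. Section 1.4 lists renal insufficiency and creatinine elevation under multiple-dose studies, and its single-dose list has neither. This trial gives one dose, so those rates are not an expected incidence here.

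Finally, ratios have a cost. If creatinine is reported to 0.1 mg/dL (assumed), a step from 0.2 to 0.3 is already 1.5-fold. There is no control arm, and concomitant vancomycin is permitted subject to the monitoring restriction in Section 4.2, so attributing a rise to the study drug would be weak. The argument concerns laboratory values, and nothing here supports extending it to vital signs or ECGs.

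**Conclusion.** The point holds as a weakness of the summary tables, not of data capture. Under Section 8.5.5 a 1.5- to 2-fold creatinine rise in a small child may read normal to normal, and the pooled mean change would barely move.

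The size depends on the assumptions. From 0.34 mg/dL the tolerated rise is 1.45- to 2.9-fold for an upper limit of 0.5 to 1.0 mg/dL. From 0.40 it is 1.24- to 2.5-fold. The 2- to 3-fold spread in baseline rests on assumed heights and equal clearance at all ages. That Section 8.5.5 names no age cohort, no ratio to baseline and no age-specific range is read directly from the text and needs no assumption.

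Safety is a secondary, descriptive objective, and the primary PK analysis is unaffected. The change is still worth making, because it uses data already collected and makes the one scheduled post-dose creatinine interpretable in each child.

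**What to change.** Amend Section 8.5.5 as follows.

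1. Present laboratory summaries by age cohort as well as overall.
2. For creatinine, add each child's Day 2/baseline ratio, with counts at 1.5 times or more and 2 times or more the child's own baseline. These are reporting categories only and trigger no action.
3. Add the change in Schwartz creatinine clearance, using Appendix 5.
4. State that local and textbook ranges must be specific to age and sex.

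The cost is a few more tables and the collection of suitable ranges from the sites, with no added blood, visits or subjects. Because ratios at very low creatinine are sensitive to rounding, show them beside the absolute values. A geometric mean ratio with a confidence interval is optional, since it would be imprecise for six infants.
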